2 ASSESSMENT AND MANAGEMENT OF RISK

All three surgical approaches (PA, PSPA, and SPAIRE) are already being used in the clinical setting. However, the use of the SPAIRE approach for THR using robotic assistance is currently limited, and extending this trial to include other sites with a MAKO robot would require training for both the PSPA and SPAIRE approach. This would include the inherent learning curves associated with adopting new technology and surgical methods. Therefore, the trial will be restricted to a single centre of excellence, where the MAKO robotic-guidance system is used in routine THR surgery, and all the surgical procedures that will be used in this trial have also been performed in routine THR surgery, both without and with robotic guidance. As such, the trial is considered to pose a risk no greater than standard medical care in this setting.

All three interventions are based on the standard PA approach, which means that it is possible to convert a PSPA or SPAIRE approach to a standard PA if required during surgery - a risk mitigation option which is available in standard care as well as in this trial.

A robust safety reporting procedure will be implemented (see section 7) such that adverse events will be detected and managed appropriately, according to established standard operating procedures.

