3 AIMS, OBJECTIVES AND OUTCOMES MEASURES

The primary aim of this trial is to investigate whether two novel robotic-assisted tendon-sparing posterior approaches (PSPA and SPAIRE) improve patient outcomes in THR compared with a robotic-assisted standard posterior approach (PA). Only patients undergoing cementless THR will be considered for the trial.

3.1 **Primary objective**

The primary objective is to determine whether there is a clinically significant between-group difference comparing PSPA vs PA, and SPAIRE vs PA for THR patients using the Oxford Arthroplasty Recovery Score (OARS) PROM at 6 weeks post-operatively, and to estimate the magnitude of any differences.

Target population	Anyone with OA of the hip requiring a total hip replacement. The trial will focus on patients suitable for a cementless acetabular component as this is appropriate for robotic guided surgery, but it will be possible to generalise the outcomes to THR procedures more generally.
Variable of interest	The primary outcome is the OARS PROM at 6 weeks post-operatively
Key intercurrent	1. Death: while alive policy: data collected up to point of death
events	2. Treatment switching: participant receives a hip replacement that is not the one they were allocated to (due to error or surgical decision at point of treatment):
	(a) treatment policy: data analysed as though intercurrent event did not occur
	(b) principal stratum: data analysed for the known subpopulation of participants who received their procedure as allocated
	3. Failure of treatment initiation: participant does not receive hip replacement at all (participant characteristics, service delivery issues):
	(a) treatment policy: cannot be applied to OARS, as only applicable post-operatively (can be applied to secondary outcomes as appropriate) (b) principal stratum: data analysed for the known subpopulation of participants who received their procedure as allocated (assumed that failure of receipt of THR would apply regardless of allocated treatment)
Population-level summary of variable	Between-group mean difference for OARS at 6 weeks post-operatively: (i) PSPA vs PA; (ii) SPAIRE vs PA

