5.2 Surgical expertise

It is a prerequisite that all treating surgeons listed on the trial delegation log have been trained to use the MAKO system, have performed a sufficient number of robotic-assisted THR procedures outside of the trial, and are familiar with the technique.

Surgeons will only be eligible to perform trial cases when they have completed the MAKO hip training course (Stryker will provide evidence to the trial team), have performed at least 12 MAKO hip cases outside of the trial, thus completing the learning curve for the MAKO robot, and they and the CI are confident that they are familiar with the technique.

Because participants in all three groups are receiving a version of the posterior approach with or without tendon preservation, if there is a clinical need to release more tendons to perform surgery safely this can be undertaken by the operating surgeon. The most common reason for conversion is if surgical exposure is insufficient and further tendon release is required to improve visualisation of the acetabulum to enable preparation and implantation of the acetabular component. This is likely to take the form of releasing one or two further tendons to improve surgical exposure. The data of any conversions will be collected; treatment switching will be accounted for using sensitivity analyses as per the estimands framework.

Surgery will be performed by seven Consultant orthopaedic surgeons in the Exeter hip unit who all have a similar experience of all three THR approaches and also the use of the MAKO robot. Only these named surgeons will perform the surgery and we do not anticipate any new surgeons joining the Research Team during the trial. The clinical team feel that there is minimal variability between

surgeons with regard to their ability in performing all three THR interventions, in terms of their patient outcomes as highlighted in the National Joint Registry.

5.3 Group 1 – THR with the standard PA and robotic guidance (Control Group)

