6.7 Trial assessments

6.7.1 Schedule of events

	Time point								
	Pre-op			Post-op					
Assessment/visit	Screening	Pre-op assessment (baseline)	7 days prior to surgery (Research Team)	24 hours prior to surgery (Surgeon & theatre staff)	Day 0/1 (inpatient)	Notes review after discharge	6 weeks (+/- 2 weeks)	6 months (26 weeks) (-4 weeks/+12 weeks)	12 months (52 weeks) (-4 weeks/+12 weeks)
Check eligibility and provide PIS	Х								
Confirm inclusion/exclusion criteria		Х							
Consent		Х							
Demographic data (name, DOB, sex of patient, height, weight, BMI, ethnicity), any existing comorbidities, and contact details		X							
Blood biomarkers – CK and CRP		Х			Х		Х		
Activity monitor issued in clinic and prepaid returns envelope provided		X					X		
PROMs – OHS, LEFS, EQ-5D-5L in clinic		Х							
Randomisation			Х	Х					
Check pre-operative imaging has been requested by surgeon (imaging to be done within 3 months of surgery date)		X							
Peri-operative data: length of stay ¹ , surgery time, blood loss, conversion of allocated randomisation approach ²						X			
PROMs – OARS, OACS, OHS, LEFS, EQ-5D-5L, SAPS in clinic							X		
Activity monitor issued via post and prepaid returns envelope provided								Х	Х
PROMs – OHS, LEFS, EQ-5D-5L, SAPS remotely								Х	Х
Additional analgesia use							Х		
Safety reporting – AEs and SAEs					Х	Х	Х	X	Х
Additional surgical procedures								X	Х
¹ Length of stay is recorded at time of discharge, i.e. converted to another during surgery (SPAIRE to PS	number of n PA or PA; or	ights a participa PSPA to PA).	int stays in	hospital post-	surgery. ² Co	nversion of a	pproach recor	ds if the intende	ed approach is

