8.5.2 Estimands framework

To fit with the estimands framework, a treatment policy approach will be used to deal with intercurrent events that relate to receipt of treatment, e.g. receipt of THR not as allocated, or failure to receive THR (for those outcomes that are valid in absence of THR). Deaths during the trial will be handled using the 'while alive' approach; participant data collected prior to death will be included in the analyses. In the event of death prior to 6-week follow-up, the outcome data will be deemed as 'non-existent' and will not be imputed.

As a sensitivity analysis, a principal stratum approach will be used, repeating the analysis including only those participants who received THR as allocated; these participants will be considered as 'always compliers' i.e. they will always receive treatment as allocated.

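### The 'principal stratum' sensitivity analysis selects on observed receipt of the allocated approach, so it does not identify always compliers and is no longer a randomised comparison

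*Protocol*

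**What the plan says.** The estimand table in section 3.1.1 defines treatment switching as the case where the "participant receives a hip replacement that is not the one they were allocated to (due to error or surgical decision at point of treatment"). It gives two strategies: treatment policy, and "principal stratum: data analysed for the known subpopulation of participants who received their procedure as allocated". Section 8.5.2 makes treatment policy the main approach. It then adds, as a sensitivity analysis, a repeat of the regression "including only those participants who received THR as allocated; these participants will be considered as 'always compliers", meaning people who would receive their allocated treatment whatever it was.

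The same subset is used again with imputed data (8.5.3), for secondary outcomes including death (8.6.2) and in the longitudinal mixed models (8.6.5). Section 5.2 confirms that switching is to be dealt with through these sensitivity analyses.

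On how switching arises, section 2 says that "it is possible to convert a PSPA or SPAIRE approach to a standard PA if required during surgery". Section 5.2 says that "if there is a clinical need to release more tendons to perform surgery safely this can be undertaken by the operating surgeon", and explains: "The most common reason for conversion is if surgical exposure is insufficient and further tendon release is required". The footnote to the schedule of events (6.7.1) lists conversions from SPAIRE to PSPA or PA and from PSPA to PA. It lists none from PA.

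**The concern.** A principal stratum is defined by what a patient would receive under every allocation, not by what was received under the actual one. In the PA arm, receiving PA says nothing about whether a tendon-sparing approach could have been completed in that patient. Membership of the always-complier stratum is therefore unobserved in PA, and calling the group a 'known subpopulation' is incorrect.

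The protocol does state an equal-across-arms assumption, but only for participants who get no hip replacement: "assumed that failure of receipt of THR would apply regardless of allocated treatment". It makes no such assumption for conversion, and its own description of conversion would contradict one.

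This is the only analysis of treatment switching in the protocol other than treatment policy. If the primary result were null, a positive result in the subset could be presented as a valid estimate of benefit in those who actually received SPAIRE or PSPA, when it may partly or wholly reflect who was removed.

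**Working it through.** **1. Who the filter keeps.** Take a patient in whom exposure through SPAIRE would be insufficient.

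| Allocated to | What happens | In the subset? |
|---|---|---|
| SPAIRE | converted to PSPA or PA | no |
| PSPA | converted to PA, or completed | depends on the patient |
| PA | PA performed (all three tendons released, section 5.3) | yes |

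The same kind of patient is dropped from one arm and kept in another, so the retained groups are not comparable by randomisation. SPAIRE versus PSPA is also affected if the two convert at different rates. Section 5.5 describes SPAIRE as limiting access more than either other approach.

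**2. The plan's own figures.** The protocol gives no conversion rate and no bias figure. Its sample size supplies the scale, and it reproduces:
- A difference of 10, SD 18.5, two-sided alpha 0.025 and 90% power give 87 per group by the noncentral t (power 0.903).
- 87/0.85 = 102.4, so 103 per group and 309 in total.
- Revised: 321/3 = 107 per arm; 107/0.95 = 112.6, so 113 per arm and 339 in total.

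**3. Bias formula.** Let p be the share who would be converted if allocated to the tendon-sparing approach. Let D be the mean OARS of non-convertible minus convertible patients on any given approach, after adjustment for sex, age group and BMI group. Assume that removals for error or non-receipt of surgery are balanced across arms.
- Filtered tendon-sparing arm: mean = m + effect, where m is the PA-treated mean of non-convertible patients.
- PA arm: mean = (1 − p) × m + p × (m − D) = m − pD.
- Difference = effect + pD, so the bias is **p × D**.

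**4. Numbers.** Both p and D are assumptions. Entries are OARS points.

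| p | D = −5 | D = 0 | D = 5 | D = 10 | D = 15 |
|---|---|---|---|---|---|
| 5% | −0.25 | 0 | 0.25 | 0.5 | 0.75 |
| 10% | −0.5 | 0 | 0.5 | 1.0 | 1.5 |
| 20% | −1.0 | 0 | 1.0 | 2.0 | 3.0 |

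Against the 10-point target, 0.25 to 3.0 points is 2.5% to 30%.

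**5. Simulation check.** Settings: 107 per arm before filtering, converted patients dropped from the tendon-sparing arm, no effect of approach for anyone, assumed total SD 19.35, 20,000 runs. The simulated bias matched p × D throughout (for example 1.00 at 10% and 10 points, 2.99 at 20% and 15 points). The treatment-policy estimate stayed within 0.03 of zero.

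The chance that the filtered analysis alone falsely favours the tendon-sparing arm at the 0.025 two-sided threshold (nominal 0.0125 in that direction) was:
- D = 0: 0.011 to 0.013
- 5%, 5 points: 0.016
- 5%, 10 points: 0.019
- 10%, 10 points: 0.029
- 20%, 10 points: 0.063
- 20%, 15 points: 0.119

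**The case against.** The strongest defence is that this is an openly specified sensitivity analysis. The treatment-policy analysis carries the primary inference, the progression criteria in section 12.2 do not name the as-allocated subset, and conversions and their reasons are recorded (sections 5 and 6.7.4). All of that stands. It limits the consequence but does not make the label correct. Nor can the point be left to the SAP, because the protocol itself fixes the selection rule.

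The defence also guards against four stronger readings that a reader might infer and that the documents do not support:

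- *The analysis is biased in favour of SPAIRE and PSPA.* That requires convertible patients to have worse 6-week OARS. It is plausible but stated nowhere. With no gap there is no bias, and with a reversed gap the sign flips.
- *Only the tendon-sparing arms lose patients.* Switching includes error, and participants who receive no hip replacement also drop out of the subset, so PA participants can be removed too. The asymmetry concerns conversion for exposure.
- *The bias is large, or it inflates the trial's error rate.* A 20% conversion rate with a 15-point gap is the top of an assumed range, and that gap exceeds the trial's own target difference. The protocol describes a single specialist centre, surgeons with similar experience of all three approaches, and PSPA as the approach most used there. High conversion is not evident. The false-positive figures above belong to the filtered analysis alone.
- *Two-stage least squares is the required replacement.* A converted patient has first had an attempted tendon-sparing approach, so allocation may affect outcome other than through the approach received. If a failed attempt costs d points and a share c converts, a null effect is estimated as −c × d/(1 − c); at c = 20% and d = 5 this is −0.2 × 5/0.8 = −1.25 points. Conversion from SPAIRE to PSPA further strains the exclusion restriction.

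**Conclusion.** The point holds as a mislabelled and non-randomised sensitivity analysis. That observed receipt fails to identify always compliers follows from the protocol's own account of conversion and needs no numerical assumption. The size and sign of the bias do need assumptions: about 0.25 to 3 OARS points for 5–20% conversion and a residual gap of 5–15 points, zero with no gap, negative if convertible patients do better. The primary treatment-policy result is not affected. This should be fixed, but it does not threaten the trial's main conclusion.

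**What to change.** In sections 3.1.1, 8.5.2 and 8.6.2, call the as-allocated subset a per-protocol analysis and remove the terms 'principal stratum', 'always compliers' and 'known subpopulation' from its description. The uses in 8.5.3 and 8.6.5 should follow. Report the number of conversions and their reasons by arm next to it.

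If a principal-stratum effect or an effect of receipt is wanted, add an estimate that does not rely on observed receipt alone. Options are instrumental variables with allocation as the instrument, or principal-score weighting on baseline predictors of conversion. State the assumptions of whichever is chosen. For instrumental variables, say that a failed attempt or a SPAIRE-to-PSPA conversion may breach the exclusion restriction.

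The cost is small. Relabelling is wording only, and conversions and reasons are already collected. The extra estimate means one more model, a wider interval and assumptions that the data cannot test. Section 8.4 has the SAP approved before database lock, so the change can be made before then.

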8.5.3 Approach to handling missing data

Missing outcome data (i.e. where the participant is not known to be deceased prior to the point of data collection) will be considered as 'missing at random'. It is also noted that OARS, OACS and SAPS are not valid outcomes for participants who do not receive THR, so will not be imputed for such participants. A multiple imputation approach will be used to impute missing outcome data. Imputation algorithms will include treatment group, minimisation variables, baseline scores (where available) for any unbalanced baseline characteristics thought to be predictive of outcome, and baseline characteristics found to be predictive of a missing primary outcome at 6-week follow-up. A sensitivity analysis will then be performed using the methods described in Sections 8.4.1 and 8.4.2 above, including both observed and imputed data, for both the treatment policy analysis and the principal stratum analysis.

8.5.4 Sensitivity analyses

Baseline descriptive data will be scrutinised for balance across the three treatment groups. Should any participant characteristics be considered unbalanced, and thought to be predictive of outcome, sensitivity analyses will be performed to adjust for these characteristics, using the methods described above.

Further sensitivity analyses will account for clustering by surgeon, by using a mixed model with a random effect on surgeon, in addition to adjustment for minimisation factors.

8.6 Analyses of secondary outcomes

8.6.1 General principles

For the secondary outcomes, the threshold for significance will be (two-sided) 0.025, and a global p-value comparing effects across all three treatment arms will be reported in addition to two-sided 95% CIs for all three pairwise comparisons; no corrections will be made for multiple testing, but p-values will be interpreted in the light of the number of comparisons being made.

Continuous PROM outcomes (OACS, SAPS, OHS, LEFS, EQ-5D-5L) will be analysed using the same principles as for OARS; OHS, LEFS and EQ-5D-5L will be collected at baseline, so baseline scores will be adjusted for. In addition, the four physical activity outcomes, the two sleep outcomes and the biomarkers, CK and CRP, will be analysed using these principles.

Time to discharge from hospital is to be measured in terms of the number of nights spent in hospital. It is anticipated that he majority of participants will be discharged on the day of surgery, so the number of nights spent in hospital will be 0. The number of nights spent in hospital will be reported descriptively by participant group, and also analysed using a negative binomial model, which will account for zero-inflation, with adjustment for minimisation variables.

Analgesia outcomes will be modelled using appropriate methods (i.e. linear regression modelling for dose outcomes and logistic regression modelling for binary outcomes).

Deaths will be reported descriptively, by allocated group, for the full period of the trial from randomisation to 12-month follow-up, and for the following time periods:

- Post-randomisation and pre-operative
- Peri-operative (within 24 hours of surgery)
- 1 day to 6 weeks post-operative
- More than 6 weeks to 52 weeks post-operative

Furthermore, the odds ratio for death (at any time during follow-up to 52 weeks post-operative) comparing PSPA vs PA, SPAIRE vs PA, and SPAIRE vs PSPA will be reported with two-sided 95% confidence intervals.

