- To compare differences between (i) PSPA vs PA and (ii) SPAIRE vs PA in terms of pain medication used in addition to the standardised prescribed post-surgery medication, immediately post-surgery and 6 week post-operatively.
- To evaluate safety of PSPA and SPAIRE approaches with respect to the PA via recorded adverse events from the day of surgery until 12 months (52 weeks) post-operatively via medical notes and post-operative follow-up at 6 weeks, 6 months (26 weeks), and 12 months (52 weeks).

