6.5 Randomisation

Participants will be randomised in a 1:1:1 ratio to SPAIRE:PSPA:PA by the ExeCTU. To promote balance across participant characteristics thought to be predictive of outcome, minimisation with a random element will be used. Characteristics of sex (male; female), age (<50; \geq 50 years) and BMI (<30; \geq 30 kg/m²) will be used in the minimisation algorithm (i.e. a total of eight combinations of minimisation factors). The operating surgeon will not be included as a minimisation factor (due to anticipated low inter-operator variability (discussed in greater detail in section 5.2), plus concern that the number of combinations of minimisation factors would be too high if surgeon is included as a factor) but a sensitivity analysis will be performed for the primary outcome measure, to investigate any operator effects.

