8 STATISTICS AND DATA ANALYSIS

8.1 Proposed sample size

The Research Team completed a pilot trial of elective THR patients, from the same population as the proposed trial population. The mean OARS score at 6 weeks post-operatively was 72.4 (N=126) in the source publication [28], compared with 72.9 in the pilot sample (N=17; 6 PSPA, 11 SPAIRE). The source publication included a combination of participants receiving hip and knee surgery; however, it is thought that OARS scores will be comparable in these groups. Whilst the mean scores were similar in the pilot sample and source publication, the standard deviation (SD) for the pilot data was higher at 24.9 compared with 17.5, which is likely due to the smaller sample size of the pilot trial. Therefore, the SD from the source publication was used to inform the sample size, with the upper bound of a one-sided 80% confidence interval (18.5) used in the calculation.

The OARS is a newly published early outcome score that currently has limited data available, and no other publications beyond the original score paper [28]. The OARS group have not yet published data regarding the Minimal Important Difference (MID, also reported as MCID – Minimal Clinical Important Difference), which is often used as the target difference for comparisons between groups.

Published data relating to the well-validated and widely used OHS by the same Oxford group, which is on a scale of 0-48, worst to best, was used to inform our figures for a reasonable MID for the OARS [33]. Although this is not ideal, this was the closest reasonable comparator available. The OHS has a corresponding MIC for an individual patient of 7.5 points and an MID of 5 points (for between-group comparisons) on the 0-48 scale [34]. Scaling up the OHS MID of 5 points to be in line with the 0-100 scale for the OARS, results in a scaled MID of 10 points, which we considered appropriate to use as a conservative target difference for sample size estimation based on OARS as the primary outcome.

To achieve 90% power to reject the null hypothesis of equal means when the population mean difference is 10 points with SD of 18.5 and with a two-sided significance level (alpha) of 0.025 (two comparisons: PSPA vs PA; SPAIRE vs PA), a total of 87 participants per treatment group is required. Allowing for a 15% drop out rate, this becomes 103 per group (309 in total).

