Having had the opportunity to review means and SDs for the primary outcome across treatment groups at an interim period during trial conduct (including data from 187 participants), it was noted that the observed SDs were higher than the SD used to inform the original sample size calculation (18.5). Based on observed SDs across treatment groups, a revised sample size of 321 participants was determined. (To maintain blinding, the observed SDs used to inform the revised sample size are not presented here, but are recorded in an unblinded area of the Trial Master File.) It was also noted that completion rate of the primary outcome was approximately 95%, well in excess of the 85% completion rate assumed in the original sample size calculation. Hence, accounting for 5% loss to follow-up the revised recruitment target is 339 participants (an increase of 30 participants, or 10% of the original recruitment target). This increased sample size was recommended by the DMC in their meeting on 03 February 2025 and endorsed by the TSC in their meeting on 10 February 2025. NIHR then approved the amendment to increase the sample size accordingly.

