8.9 Adverse events analyses

SAEs will be reported descriptively by treatment as received (with footnotes to indicate where treatment received was not as allocated).

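### The only safety contrast given an interval, the odds ratio for death, can easily be infinite or undefined at 113 per arm; a score-based risk difference should lead

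*Protocol*

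**What the plan says.** The safety objective in protocol section 3.2 is comparative: "To evaluate safety of PSPA and SPAIRE approaches with respect to the PA", using adverse events recorded from the day of surgery to 52 weeks.

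Two sections say how safety will be analysed. Section 8.9 states that "SAEs will be reported descriptively by treatment as received". Section 8.6.1 tabulates deaths by allocated group, overall and in four time windows. It then adds "the odds ratio for death (at any time during follow-up to 52 weeks post-operative) comparing PSPA vs PA, SPAIRE vs PA", and SPAIRE vs PSPA, with two-sided 95% confidence intervals. Section 8.6.2 applies the treatment policy and principal stratum approaches to death.

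The protocol states no expected death rate, no safety margin and no interval method for this odds ratio. On numbers, section 6.5 says "Participants will be randomised in a 1:1:1 ratio to SPAIRE:PSPA:PA" and section 8.1 says "accounting for 5% loss to follow-up the revised recruitment target is 339 participants".

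**The concern.** The protocol fixes its one interval-based safety contrast on death, which is likely to be rare after elective surgery, and on a ratio scale that breaks down when an arm has no events. With no deaths in the tendon-sparing arm the odds ratio is 0. With none in the reference arm it is infinite and has no finite upper limit. With none in either it is undefined.

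What is at stake is the use of the result. A comparative safety objective needs a statement of how large an excess is still compatible with the data. If the reference arm has no deaths, the specified measure cannot give that statement, although the counts would support one on the absolute scale.

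**Working it through.** **Arm size.** Section 8.1 plans for 90% power; its other inputs read: "the population mean difference is 10 points with SD of 18.5 and with a two-sided significance level (alpha) of 0.025". A noncentral-t calculation gives power 0.8992 at 86 per group and 0.9028 at 87, so the protocol's 87 is reproduced. 87/0.85 = 102.4, so 103 per group and 3 x 103 = 309. For the revision, "a revised sample size of 321 participants was determined": 321/3 = 107; 107/0.95 = 112.6, so 113 per arm; 3 x 113 = 339. The arm size for deaths is therefore n = 113.

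**Chance of an arm without deaths.** Let p be the 52-week death risk, equal in both arms. The documents give no value, so the range below is assumed.

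- One named arm (for example the reference arm) has no deaths: q = (1 - p)^113
- At least one arm of a pair has none: 1 - (1 - q)^2
- Both arms have none: q^2
- At least one of the three arms has none: 1 - (1 - q)^3

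At p = 1%: q = 0.99^113 = 0.321; 1 - 0.679^2 = 0.539; 0.321^2 = 0.103; 1 - 0.679^3 = 0.687.

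| Assumed p | Expected deaths per arm | Reference arm zero (no finite upper limit) | Pair has a zero arm | Both zero (undefined) | Any of three arms zero |
|---|---|---|---|---|---|
| 0.25% | 0.28 | 75% | 94% | 57% | 98.5% |
| 0.5% | 0.57 | 57% | 81% | 32% | 92% |
| 1% | 1.13 | 32% | 54% | 10% | 69% |
| 2% | 2.26 | 10% | 19% | 1% | 28% |
| 3% | 3.39 | 3% | 6% | 0.1% | 9% |

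The pair probability passes 50% when q = 1 - sqrt(0.5) = 0.293, that is p = 1 - 0.293^(1/113) = 1.1%. The exact arm size matters little: with 107 per arm and p = 1%, q = 0.99^107 = 0.341 and 1 - 0.659^2 = 57%.

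**What each measure reports.** Deaths are tendon-sparing v reference, 113 per arm. The odds-ratio interval is exact conditional. The risk-difference interval is Newcombe, in percentage points.

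| Deaths | Odds ratio (95% interval) | Risk difference (95% interval) |
|---|---|---|
| 0 v 0 | undefined (0 to infinity) | 0 (-3.3 to +3.3) |
| 1 v 0 | infinite (0.026 to infinity) | +0.9 (-2.5 to +4.8) |
| 2 v 0 | infinite (0.19 to infinity) | +1.8 (-1.8 to +6.2) |
| 0 v 1 | 0 (0 to 39) | -0.9 (-4.8 to +2.5) |
| 1 v 1 | 1.0 (0.013 to 79) | 0 (-4.0 to +4.0) |
| 2 v 1 | 2.0 (0.10 to 120) | +0.9 (-3.3 to +5.4) |

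The 0 v 0 case can be checked by hand. The Wilson upper limit for 0/113 is 1.96^2/(113 + 1.96^2) = 3.84/116.84 = 3.29%, and the Newcombe limits are then plus and minus 3.29 points.

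**The case against.** Four points on the other side have force.

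- **The protocol does ask for 95% intervals, and exact ones can be used.** This stands. A reader might infer that the odds ratio never bounds harm, or loses its bound whenever either arm has no deaths. That is wrong: with 0 v 1 and 0 v 2 deaths the exact upper limits are 39 and 5.3. The limit is lost only when the reference arm has no deaths.
- **How often this happens depends on a rate the protocol does not give.** This stands. The pair probability runs from 94% to 6% over assumed mortality of 0.25% to 3%, so frequent failure can be claimed only at about 1% or below.
- **The interval method belongs to the statistical analysis plan.** This stands for the method, and its absence is no fault here. The choice of effect measure is different, because the protocol has already fixed it. Where the reference arm has no deaths, an exact interval for that measure still has no finite upper limit.
- **Deaths are also tabulated by arm, so a reader could work out the risk difference.** True, and it limits the weight of the point. A prespecified measure is still better than leaving readers to derive one.

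A reader might also infer that the plan will declare the approaches equally safe because the difference in deaths is not significant, or that the comparison is at fault for low power. The documents support neither. Section 8.6.1 does set a general 0.025 threshold for secondary outcomes, but its sentence on deaths asks for estimates and intervals. No section bases a safety conclusion on non-significance, and none presents death as a powered comparison. Section 7.3 adds periodic review of serious adverse events by the steering and monitoring committees. A risk difference would not raise power either.

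**Conclusion.** The point holds as a weakness in the choice of measure, not as an error in the protocol's arithmetic. The only safety contrast with a specified estimate and interval uses a scale that fails when an arm has no deaths. At 113 per arm a given pair has such an arm with probability 81%, 54% and 19% at mortality of 0.5%, 1% and 2%, and the upper limit is not finite with probability 57%, 32% and 10%. These figures assume equal risk in both arms, independent patients and death rates that are not in the documents. Above about 2% mortality the problem is minor. The remedy is cheap and should be made before database lock, by which time section 8.4 requires the statistical analysis plan to be approved.

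**What to change.** In section 8.6.1, and in the statistical analysis plan to match:

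1. For each of the three pairs, report the absolute risk difference in deaths to 52 weeks with a score-based 95% interval (Newcombe or Miettinen-Nurminen, one of them named in advance) as the main measure.
2. Keep the odds ratio as a supplementary figure with an exact interval, marked as not estimable where both arms have no deaths.
3. State that the upper limit of the risk difference shows what excess in deaths the trial does not exclude, and that an interval including zero is not evidence of equal safety.

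This needs no new data. It costs a change of wording and one more estimate per pair. The report must also say openly that an excess of about 3 to 5 percentage points may not be excluded (upper limits of 3.3, 4.0, 4.8 and 5.4 for 0 v 0, 1 v 1, 1 v 0 and 2 v 1 deaths). The change adds no power and leaves the descriptive reporting of serious adverse events in section 8.9 as it is.
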